A study of safety and efficacy of Transcutaneous Afferent Patterned Stimulation (TAPS) for reduction of action tremor in Parkinson's Disease (PD)	Protocol PD-02
	Rev A; 1-OCT-2020

**A STUDY OF SAFETY AND EFFICACY OF TRANSCUTANEOUS AFFERENT PATTERNED STIMULATION
(TAPS) FOR REDUCTION OF ACTION TREMOR IN PARKINSON'S DISEASE (PD)**

**PROTOCOL PD-02
1-OCT-2020**

REV A

Cala Health, Inc.
[name]
[name]

A study of safety and efficacy of Transcutaneous Afferent Patterned Stimulation (TAPS) for reduction of action tremor in Parkinson's Disease (PD)	Protocol PD-02
	Rev A, 1-OCT-2020

**A study of safety and efficacy of Transcutaneous Afferent Patterned Stimulation (TAPS)
for reduction of action tremor in Parkinson's Disease (PD)**

PD-02

SPONSOR SIGNATURE PAGE

Prepared by:

28-OCT-2020

[name]

Date

Approved by:
Clinical Affairs

27-OCT-2020

[name]

Date

Regulatory Affairs

10/28/2020

[name]

Date

A study of safety and efficacy of Transcutaneous Afferent Patterned Stimulation (TAPS) for reduction of action tremor in Parkinson's Disease (PD)	Protocol PD-02
	Rev A, 1-OCT-2020

CLINICAL STUDY SYNOPSIS

Study Objective	
Title	A study of safety and efficacy of Transcutaneous Afferent Patterned Stimulation (TAPS) for reduction of action tremor in Parkinson's Disease (PD)
Study Device	Cala Trio
Objective	Demonstrate safety and efficacy of TAPS delivered by the Cala Trio™ device as a treatment for action tremor in subjects with Parkinson's disease hand tremor.

Study Design Elements	
Study Design	Single arm study
Overview of Study Visits and Procedures	This study will include both subjects on levodopa and subjects taking other Parkinson's medications/unmedicated for Parkinson's. Subjects will be screened for eligibility and fitted with a Cala Trio device. Due to COVID-19 social distancing requirements, visits requiring physician or subject rated assessments will be conducted via telemedicine (i.e., video call). During Visit 1 (Day -7), enrollment will consist of subject eligibility/screening using clinician rated UPDRS assessments. During Visit 2a (Day -1), subjects will receive device training and calibration instructions. During Visit 2b (Day 0), UPDRS assessments and ability to conduct ADLs will be assessed pre and post stimulation session. Visits 2a and 2b may be combined into a single visit. Subjects will use Cala Trio at home for a period of 4 weeks (Day 1- Day 28). During Visit 3 (Day 28), the subjects will exit the study after a UPDRS and ADLs assessment pre and post stimulation session.
Efficacy Assessments	
 • Primary: Within subject comparison of tremor power before stimulation to after stimulation in dominant arm • Secondary: Within subject comparison of ADLs and UPDRS across Visits 1-3
Safety	The safety of the peripheral nerve stimulation will be characterized by the incidence of device and therapy-related adverse events
Number of Subjects	Up to 60 subjects
Number of Sites	1 site
Study Participation	The length of study participation is up to 6 weeks

Subject Population	
Inclusion Criteria	
Prospective subjects must meet all of the following criteria to be eligible for study participation:
 
 • Must be ≥ 22 years of age • Competent and willing to provide written, informed consent to participate in the study • Clinically significant postural tremor as defined by: 
 ◦ Dominant hand/arm exhibiting postural tremor ≥ 2 (while in the off state) as assessed by the MDS-UPDRS postural tremor score • Stable dose of Parkinson's disease medications, if applicable, for 30 days prior to study entry • Willing to comply with study protocol requirements including: 
 ◦ Having the ability to do telemedicine or video calls for study visits ◦ remaining on a stable dosage of Parkinson's medications, if applicable, during the duration of the study ◦ no significant caffeine consumption within 8 hours of study visits
Exclusion Criteria	
Prospective subjects who meet any of the following criteria are not eligible for enrollment in this study:
 
 • Implanted electrical medical device, such as a pacemaker, defibrillator, or deep brain stimulator • Suspected or diagnosed epilepsy or other seizure disorder • Swollen, infected, inflamed areas, or skin eruptions, open wounds, or cancerous lesions of skin at stimulation site • Peripheral neuropathy affecting the tested upper extremity • Presence of any other neurodegenerative disease or dementia. These may include: multisystem atrophy, progressive supranuclear palsy, dementia with Lewy bodies, and Alzheimer's disease. • Botulinum toxin injection for hand tremor within 6 months prior to study enrollment • Are participating or have participated in another interventional clinical trial in the last 30 days which may confound the results of this study, unless approved by the Sponsor • Significant caffeine consumption within 8 hours of study enrollment, which may confound the results of the study, where significant caffeine is considered more than 95 mg (equivalent to a cup of coffee). • Subjects unable to communicate with the investigator and staff • Any health condition that in the investigator's opinion should preclude participation in this study • Pregnancy or anticipated pregnancy during the course of the study

A study of safety and efficacy of Transcutaneous Afferent Patterned Stimulation (TAPS) for reduction of action tremor in Parkinson's Disease (PD)	Protocol PD-02
	Rev A, 1-OCT-2020

Study Contacts	
Sponsor	
Cala Health, Inc. [name] [name]
 
Contact: [name] Director of Clinical Operations [contact] [contact]

A study of safety and efficacy of Transcutaneous Afferent Patterned Stimulation (TAPS) for reduction of action tremor in Parkinson's Disease (PD)	Protocol PD-02
	Rev A, 1-OCT-2020

Table of Contents

1.0 Introduction	1
1.1 Scientific Background.....	1
2.0 Device Description	2
2.1 Intended Use	2
2.2 Instruction for Use and Labeling.....	3
3.0 Study Design.....	4
3.1 Overview	4
3.2 Study Objectives	4
3.3 Inclusion Criteria.....	4
3.4 Exclusion Criteria.....	4
3.5 Study Assessments	5
3.6 Safety	5
3.7 Blinding	5
3.8 Sample Size	5
3.9 Study Design Schematic.....	6
3.10 Subject Recruitment.....	6
3.11 Pre-Screening/Scheduling	6
3.12 Informed Consent.....	6
3.13 Screening	6
3.14 Enrollment	7
3.15 Visit 1.....	7
3.16 Visit 2.....	7

1.0 Introduction

Idiopathic Parkinson's disease (PD) is characterized by the cardinal motor signs and symptoms of rest tremor, bradykinesia and muscle rigidity. The perception of most PD clinicians is that of these, bradykinesia is the most disabling symptom in early and moderate PD (balance/gait difficulties and cognitive impairment are almost universally agreed to be the most disabling feature in more advanced PD). The classic teaching of treatment for PD tremor is that because it is predominant at "rest" and often resolves with movement and when reaching for a target, it is not functionally very disabling and therefore should not be a focus of therapeutic outcomes. However, for a substantial number of people with PD, the postural and kinetic components of their tremor are indeed disabling.

Further, of all of the cardinal motor features of PD, tremor is the most resistant in response to dopaminergic therapies [1-2]. For many with disabling PD tremor, the only effective therapeutic alternative is Deep Brain Stimulation (DBS), which is a highly invasive procedure.

The Cala Trio device may offer patients with PD a novel non-pharmacological, non-invasive alternative, in the form of stimulation of peripheral nerves, to aid in action hand tremor relief. This highly innovative form of therapy will have important health, quality of life, and economic benefits for PD patients.

1.1 Scientific Background

Transcutaneous electrical nerve stimulation (TENS) is a form of noninvasive stimulation of peripheral nerves that has been shown to be safe and effective in treating various pain syndromes [3-6]. The mechanism of TENS is thought to be modulation of sensory input at the level of the spinal cord or brain.

Traditional TENS and DBS use continuous, fixed-frequency stimulation; however, accumulating evidence suggests that patterned electrical stimulation may improve the therapies' selectivity and effectiveness [7-10]. There is also specific evidence supporting the use of an alternating stimulation pattern for tremor reduction [11]. Peripheral nerve stimulation at the wrist activates neural networks similar to those responsible for the therapeutic mechanism of DBS in suppressing tremor [12-13]. Furthermore, recent literature suggests that the timing of stimulation in relation to the tremor is critical for effective tremor suppression [14-15].

Based on this research, Cala Health developed the Cala Trio device, which delivers alternating bursts of transcutaneous electrical stimulation to the radial and median nerves at the wrist. The stimulation is tremor-customized, meaning that each nerve receives bursts of stimulation at the patient's measured tremor frequency. This new form of non-invasive peripheral nerve stimulation is called transcutaneous afferent patterned stimulation (TAPS). TAPS is designed specifically to relieve hand tremor symptoms in patients with essential tremor (ET). The purpose of this study is to demonstrate the safety and efficacy of TAPS' utility in the new indication of PD.

2.0 Device Description

2.1 Intended Use

The Cala Trio device (Figure 1) is an investigational device designed for the delivery of Transcutaneous Afferent Peripheral Stimulation (TAPS). The device is to be used only in accordance with the approved investigational plan and requires informed consent.

2.1.1 Cala Trio Device

The Cala Trio device is designed to deliver TAPS to the median and radial nerves of the wrist on which it is worn. The device system includes three components listed below; details about these components follow.

Stimulator – a body worn stimulator which snaps into a wristband to apply a customized stimulation pattern to the median and radial nerves of an individual;

Band – a wristband with embedded multi-use electrodes which conduct the stimulation. Unlike standard hydrogel electrodes, the multi-use electrodes are not limited to single use and may be repeatedly used by the same subject;

Base station – a charging base station which charges the device and may upload device data to a secure cloud platform.

[figure not shown]

Figure 1. Cala Trio device components

A study of safety and efficacy of Transcutaneous Afferent Patterned Stimulation (TAPS) for reduction of action tremor in Parkinson's Disease (PD)	Protocol PD-02
	Rev A; 1-OCT-2020

2.1.2 Stimulator

The stimulator contains the electronics for providing TAPS and was designed with careful considerations of use by subjects with hand tremors. There are 3 easy-to-press buttons (Figure 1) on the stimulator that are used for calibration and stimulation amplitude adjustment, among other functions. Text prompts, stimulation delivery parameters, and other messages are provided on a full color display to provide instructions and stimulation delivery information to the clinician and subject throughout device use. A countdown timer automatically terminates the delivery of stimulation after a 40-minute treatment session. The stimulator is powered by a rechargeable battery, which can be recharged through the base station (see additional details below). The stimulator produces charge-balanced, current-controlled, biphasic, square waveforms. The duration of the primary (depolarizing) phase is 300 μ sec, the frequency is 150 Hz, and the maximum current is 8 mA. The current is delivered to alternating electrode pairs in the band that target the median and radial nerves of the subject. The stimulation alternates between electrode pairs at the subject's tremor frequency (4 - 12 Hz), which is measured during a calibration procedure while the subject performs a tremor-inducing task. The tremor frequency is measured by motion sensors contained within the stimulator which gather kinematic data.

2.1.3 Band

Bands are constructed from a microfiber material with connectors to interface with the stimulator and a Velcro fastener to comfortably secure the device to the subject's wrist, much like a wristwatch.

There are multiuse electrodes are embedded in the band. The electrodes allow for good electrical conduction to the subject's skin. Unlike standard hydrogel electrodes, the electrodes are not limited to single use and may be repeatably used by the same subject for up to 90 consecutive days.

The electrodes are spaced at appropriate intervals around the circumference of the band in order to target the median and radial nerves properly. To accommodate a broad distribution of wrist sizes, the band has three sizes (small, medium, and large). The band is also right or left-handed to target the appropriate nerves of the prescribed hand with tremor.

2.1.4 Base Station

The base station is supplied with the Cala Trio device. For safety considerations, the Cala Trio device is designed such that it cannot be mechanically connected to the base station when it is worn by a subject (e.g., during stimulation delivery). The Cala Trio device is charged through the base station, which may be connected to a secure cloud platform which stores device data (e.g. kinematic data and usage information).

2.2 Instruction for Use and Labeling

The Cala Trio device will be used in accordance with its instructions for use.

The labeling on the Cala Trio device includes the statement, "CAUTION: Investigational Device. Limited by United States law to investigational use", as required by United States federal regulations.

A study of safety and efficacy of Transcutaneous Afferent Patterned Stimulation (TAPS) for reduction of action tremor in Parkinson's Disease (PD)	Protocol PD-02
	Rev A; 1-OCT-2020

3.0 Study Design

3.1 Overview

This is a single arm study done involving telemedicine visits and a home use period. Subjects will be seen for up to 4 telemedicine visits and will have a 4 week treatment period at home. During the treatment period, subjects will be asked to stimulate their dominant hand at home 2 times per day, preferably at the same time every day, measuring kinematics before and after every therapy session.

This study will include both subjects on levodopa and subjects taking other Parkinson's medications/unmedicated for Parkinson's.

3.2 Study Objectives

The study objective is to demonstrate safety and efficacy of TAPS delivered by the Cala Trio™ device as a treatment for action hand tremor in subjects with Parkinson's disease.

3.3 Inclusion Criteria

Prospective subjects must meet all of the following criteria to be eligible for study participation:

- Must be ≥ 22 years of age
- Competent and willing to provide written, informed consent to participate in the study
- Clinically significant postural tremor as defined by:
 - Dominant hand/arm exhibiting postural tremor ≥ 2 (while in the off state) as assessed by the MDS-UPDRS postural tremor score
- Stable dose of Parkinson's disease medications, if applicable, for 30 days prior to study entry
- Willing to comply with study protocol requirements including:
 - remaining on a stable dosage of Parkinson's medications, if applicable, during the duration of the study
 - no significant caffeine consumption within 8 hours of study visits
 - Having the ability to do telemedicine or video calls for study visits

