3.4 Exclusion Criteria

Prospective subjects who meet any of the following criteria are not eligible for enrollment in this study:

- Implanted electrical medical device, such as a pacemaker, defibrillator, or deep brain stimulator
- Suspected or diagnosed epilepsy or other seizure disorder
- Swollen, infected, inflamed areas, or skin eruptions, open wounds, or cancerous lesions of skin at stimulation site
- Peripheral neuropathy affecting the tested upper extremity
- Presence of any other neurodegenerative disease or dementia. These may include: multisystem atrophy, progressive supranuclear palsy, dementia with Lewy bodies, and Alzheimer's disease.
- Botulinum toxin injection for hand tremor within 6 months prior to study enrollment
- Are participating or have participated in another interventional clinical trial in the last 30 days which may confound the results of this study, unless approved by the Sponsor

A study of safety and efficacy of Transcutaneous Afferent Patterned Stimulation (TAPS) for reduction of action tremor in Parkinson's Disease (PD)	Protocol PD-02
	Rev A; 1-OCT-2020

- Significant caffeine consumption within 8 hours of study enrollment, which may confound the results of the study, where significant caffeine is considered more than 95 mg (equivalent to a cup of coffee).
- Subjects unable to communicate with the investigator and staff
- Any health condition that in the investigator's opinion should preclude participation in this study
- Pregnancy or anticipated pregnancy during the course of the study

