3.17 Home-Usage

A study of safety and efficacy of Transcutaneous Afferent Patterned Stimulation (TAPS) for reduction of action tremor in Parkinson's Disease (PD)	Protocol PD-02
	Rev A; 1-OCT-2020

The home use portion of the study will last 4 weeks. It will include:

- 2 stimulation sessions/day preferably at the same time every day-recommended as one in the morning and one in the evening.
- Motion Data on device before and after each stimulation session. Cala Trio will direct the subject to perform postural hold tremor tasks before and after the stimulation session to measure tremor power. Additionally, subjects will input their Patient Session Impression of Improvement (PSI-I) rating on the device after the stimulation session
- Weekly Bain & Findley Activities of Daily Living (ADL) upper limb subset score will be rated by the subject based on their recall of the previous week (no props will be used)
- Device factory reset of the Cala Trio will occur on Day 14 of treatment via a call with study staff

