3.18 Visit 3/Study exit

Subjects will be reminded to be in the *off* state, i.e. to skip their last dose of PD medication, prior to their telemedicine Visit 3/Study exit. The subject will be asked to not stimulate at least 8 hours prior to this visit. The subject will receive a single 40-minute therapy session with their Cala Trio. The following assessments will be made prior to the therapy session and again immediately post the therapy session:

- Tremor assessments (while in the *off* state) including:
 - Modified MDS Unified Parkinson's Disease Rating Scale Part III (MDS-UPDRS) be rated by the PI
 - Bain & Findley Activities of Daily Living (ADL) upper limb subset score will be rated by the subject. The ADL assessment will be performed using the subject's own household props
- CGI-S, I/PGI-S, I
 - Clinical/Patient Global Impression of Severity (CGI-S/PGI-S): The investigator or designee (CGI) and Patient (PGI) will rate the overall tremor severity prior to stimulation
 - Clinical/Patient Global Impression of Improvement (CGI-I/PGI-I): The investigator or designee (CGI) and Patient (PGI) will rate the overall tremor improvement following stimulation
- Product/preference survey
- Subjects will return all study materials with provided shipping packages

A factory device reset and re-calibration may be required if the device does not prompt a tremor task measurement of postural hold prior to starting the stimulation session.

All subjects will be informed of their right to withdraw from the clinical study at any time without penalty or loss of benefits. The Investigator may prematurely discontinue any subject from the study if the Investigator feels that the subject can no longer fully comply with the requirements of the study or if any of the study procedures are deemed potentially harmful to the subject.

A study of safety and efficacy of Transcutaneous Afferent Patterned Stimulation (TAPS) for reduction of action tremor in Parkinson's Disease (PD)	Protocol PD-02
	Rev A; 1-OCT-2020

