3.2 Analysis Populations

As stated in section 2.2, available data on all enrolled subjects will be summarized and reported, referred to in ICH E9 (“Statistical Principles for Clinical Trials”) as the *full analysis set*.

Two analysis populations will be defined, one consisting of all available data evaluated under intent-to-treat (ITT) principles, and the other consisting of all available data evaluated under per-protocol (PP) principles. Both populations are defined in further detail below. For each analysis population, “available data” means that missing data will not be replaced or imputed, and that endpoints defined as change scores will require both baseline and follow-up data to be present to be included in analyses.

The ITT population consists of all enrolled subjects.

The PP population is defined as ITT subjects who furthermore:

- Met all inclusion/exclusion criteria (in particular, subjects enrolled but determined post-enrollment not to have met one or more eligibility criteria will be excluded from the PP population).
- Were dispensed a stimulator at the primary timepoint (visit 2b) that had been appropriately calibrated to the subject’s tremor; subjects who were dispensed stimulators at the time of visit 2b that had not been calibrated to that subject’s tremor will be excluded from the PP population.
- Remained on a stable dosage of tremor and antidepressant medications, if applicable, during the duration of the study.
- Were rated by a certified UPDRS rater at the primary timepoints (Visit 1, Visit 2b and Visit 3).

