3.9 Effectiveness Outcomes

The effectiveness of the Cala Trio device in reducing action hand tremor symptoms in PD will be evaluated by the following:

Primary Effectiveness Endpoints

- Tremor power (kinematic response), as collected with the device during postural holds (outstretched or wing beating), change from pre-stimulation to post-stimulation across sessions. (See section 3.3 for detailed description).

This endpoint will be tested statistically using hypotheses as defined above.

Secondary Effectiveness Endpoint

- Improvements in MDS-UPDRS action tremor and BF-ADL upper limb subset scores, relevant to the stimulated upper limb, from pre- to post-stimulation (i.e., acute improvement from stimulation)
- Improvements in MDS-UPDRS action tremor and BF-ADL upper limb subset scores, relevant to the stimulated upper limb, from baseline (pre-stimulation Visit 2b) to study exit (post-stimulation Visit 3) (i.e., accumulated baseline improvement from one month therapy + acute improvement from stimulation)
- Improvements in pre-stimulation MDS-UPDRS action tremor and BF-ADL upper limb subset scores, relevant to the stimulated upper limb, from baseline (pre-stimulation Visit 2b) to last session (pre-stimulation Visit 3) (i.e., accumulated baseline improvement from one month therapy)

These endpoints will be tested statistically using hypotheses as defined above (See section 3.4 for details).

Additional Exploratory Endpoints, Clinical Data

- Raw change from pre-stimulation to post-stimulation, assessed separately for Visit 2b and Visit 3, for each of the following:
 - Per-task MDS-UPDRS Part III score
 - Per-task BF-ADL upper limb subset score
- % Subjects that had a ≥ 0.5 -point average per-task improvement in MDS-UPDRS Part III total score (six tasks, relevant to the stimulated upper limb) from pre-stimulation to post-stimulation, assessed separately for Visit 2b and Visit 3
- % Subjects that had a ≥ 0.5 -point average per-task improvement in BF-ADL upper limb subset score (nominally eight tasks, relevant to the stimulated upper limb) from pre-stimulation to post-stimulation, assessed separately for Visit 2b and Visit 3
- Per-task improvements in MDS-UPDRS Part III and BF-ADL from pre-stimulation to post-stimulation, assessed separately for Visit 2b and Visit 3 as follows:
 - Number of patients who had a pre-stimulation score ≥ 2 for that task

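### The 8-hour no-stimulation hold before Visits 2b and 3 is missing from the per-protocol rule, so residual acute effect could enter endpoints 3a and 3b as one-month benefit

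*Protocol*

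**What the plan says.** **The hold.** Protocol 3.16.2 (Visit 2b) and 3.18 (Visit 3) carry the same sentence: "The subject will be asked to not stimulate at least 8 hours prior to this visit". The SAP repeats it in 2.1. Table 1 in Protocol 4.0 has no line for recording time since the last session.

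**Home use.** Protocol 3.17 calls for "2 stimulation sessions/day preferably at the same time every day-recommended as one in the morning and one in the evening". Table 1 puts home use on Days 1 to 28 and Visit 3 on Day 28 with a window of +7 days, so Day 28 can be both.

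**Per-protocol rule.** SAP 3.2 begins "The PP population is defined as ITT subjects who furthermore" and lists four conditions: eligibility, a calibrated stimulator at Visit 2b, stable tremor and antidepressant medication, and a certified rater. SAP 3.6 says the primary and secondary endpoints are tested in both the ITT and the PP population.

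**Endpoints.** In SAP 3.4, endpoints 3a (MDS-UPDRS) and 3b (BF-ADL) compare Visit 2b pre-stimulation with Visit 3 pre-stimulation. SAP 3.9 describes them as "accumulated baseline improvement from one month therapy". Endpoints 1b and 1d are the pre-to-post changes within Visit 3.

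**Caffeine.** Protocol 3.3 requires willingness to comply with "no significant caffeine consumption within 8 hours of study visits". Protocol 3.4 excludes "Significant caffeine consumption within 8 hours of study enrollment, which may confound the results of the study", with the limit set at 95 mg. The procedures for Visits 2b and 3 do not mention caffeine.

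**The concern.** Reading 3a and 3b as accumulated benefit requires a Visit 3 pre-stimulation score free of the acute effect of a recent session. The hold serves that purpose. The product survey asks how long the effect lasts after stimulation ends (SAP 3.9), so the plan treats persistence as possible. Yet no analysis rule uses the hold.

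A breach is foreseeable. When Visit 3 falls on Day 28, a subject who keeps to the usual morning session and is seen within 8 hours of it is in breach. That rating then counts in both ITT and PP. The study has one arm and no blinding, so no control group would reveal the shift.

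Two effects follow if some acute benefit persists. It lowers the Visit 3 pre-stimulation score and so moves 3a and 3b toward benefit. It also shrinks 1b and 1d, and all of 1a to 1d must be significant before 2a and 2b, and then 3a and 3b, may be tested (SAP 3.4).

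**Working it through.** **1. Does any rule remove a rating made in breach?** The four PP conditions in SAP 3.2 do not. The only spacing rule is in SAP 3.3: a session must start at least 2 hours after the previous one ended. That rule governs kinematic sessions for the primary endpoint, not clinical ratings. SAP 3.4 drops a rating only for missing task scores. So no rule does.

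**2. Sample size used.** The plan's lower figure reproduces: 30 / (1 − 0.10) = 33.3, rounded up to 34. For the upper end, 50 × 0.90 = 45 analysed. The point does not depend on either figure.

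**3. Effect on 3a, tested alone.** Let f be the share of subjects in breach, c the residual acute effect in points, and SD the standard deviation of the pre-to-pre change. All three are assumptions. The true one-month change is set to 0.

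- Bias = f × c = 0.20 × 0.25 = 0.05 points.
- Total SD = √(SD² + f(1 − f)c²). For SD 0.4: √(0.16 + 0.01) = 0.412. For SD 0.6: √(0.36 + 0.01) = 0.608.
- Noncentrality = bias × √45 / total SD = 0.81 and 0.55.
- Chance that t with 44 df exceeds 2.015 (two-sided 0.05, favourable side) = 12.2% and 7.8%, against 2.5% with no breach. Simulation gives 12.1% and 7.7%.
- At N = 34 the same inputs give about 10% and 7%.
- Over f = 10 to 30%, c = 0.15 to 0.5 and SD 0.4 to 0.6, the range is about 3.6% to 57%.

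**4. Effect of gatekeeping.** I simulated 3a conditional on 1a to 1d and 2a to 2b all being significant, with f = 0.20 and c = 0.25. Further assumptions: the primary endpoint is met, the SD of the acute change is 0.5, the two scales are independent, and the residual reduces the Visit 3 acute change by c.

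| True acute effect (points) | 3a favourable, SD 0.4 | 3a favourable, SD 0.6 |
|---|---|---|
| 0.25 | 4.3% | 2.3% |
| 0.35 | 10.7% | 5.9% |
| 0.50 | 12.3% | 7.9% |

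Correlation between the scales would raise the first row somewhat. Gatekeeping never raises the figure beyond simulation error.

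**5. Effect on 1b.** Take the extreme case, in which breaching subjects show no further acute change at Visit 3. The standardized effect d then becomes d(1 − f). At N = 45 and d = 0.5, power falls from 0.91 to 0.75 (f = 20%) or 0.63 (f = 30%). At d = 0.7 it falls from 0.996 to 0.96 or 0.90.

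**The case against.** Several points on the other side stand.

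- **The documents do not show that breaches will happen or that effect persists.** They give no breach rate and no size or duration of residual effect. Visit 3 may fall up to 7 days after Day 28. A morning visit after an evening session can satisfy the hold, and subjects are asked to keep it.
- **Breaches could be detected.** Device usage data are stored (Protocol 2.1.4), and the deviation list in Protocol 8.1 is open-ended. The gap is that no analysis rule uses this information.
- **A PP condition does not protect the main analysis.** SAP 3.12 makes the full analysis set the primary cohort. Changing PP alone leaves any bias there, so the fix needs a sensitivity analysis in that set too.
- **The scope is limited.** Study success rests on the primary per-session kinematic ratio. Endpoints 2a and 2b end post-stimulation and are already described as accumulated plus acute. Shrinkage of 1b and 1d works against the device.

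A reader might also infer that the caffeine conditions lie wholly outside the PP rule. The documents do not support that. Caffeine before enrollment is an exclusion criterion, and so enters through "Met all inclusion/exclusion criteria". Only caffeine before Visits 2b and 3 is left out. Uneven intake could shift a change score either way, so no direction of bias is claimed, and the caffeine text is not evidence for carry-over.

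**Conclusion.** The gap is real and narrow. The protocol states a measurement condition for the rated visits, and the PP definition does not apply it. A Visit 3 rating made soon after a session is therefore kept in the planned PP test of 3a and 3b.

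Whether this produces bias depends on breaches occurring and acute effect persisting, and the documents quantify neither. Under the stated illustration the false-positive chance for 3a is about 8 to 12% ungated. After gatekeeping it is about the same when acute effects are large and falls to around 2 to 4% when they are small.

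A reader might take the 57% corner as the expected size. That would be wrong. It needs 30% of subjects to carry a 0.5-point residual, which equals the SAP's own exploratory threshold for a responder (3.9), and it ignores gatekeeping. Nor do the documents support reading this as a threat to the primary endpoint. The case for change is that the remedy is cheap and makes a planned analysis cleaner.

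**What to change.** 1. Take the time of the last session before Visits 2b and 3 from the device log. The 2-hour rule in SAP 3.3 already needs session times.
2. Add to SAP 3.2: for visit-based endpoints, the PP analysis includes only visits that meet the protocol's 8-hour no-stimulation condition. State whether the brief stimulation used to set intensity in training counts, since Visits 2a and 2b may be combined.
3. Report the number of breaching visits. Present 3a and 3b in the full analysis set with and without them, as a sensitivity analysis.
4. Secondarily, record at Visits 2b and 3 whether the protocol's visit caffeine condition was met, and treat it in the same way.
5. The sponsor should reconcile the Day 28 home-session instruction with the 8-hour hold.

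The cost is one look-up, one case report form question at two visits, and a few lines in the SAP. The downside is a slightly smaller PP set for the secondary endpoints.
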